## 6. METHODOLOGY

- **Study Design:** Two-group parallel Randomized Controlled Trial (RCT) with a 1:1 allocation ratio.
- **Setting:** Hemodialysis units in Iraq.
- **Sample Size:** 70 adult patients receiving MHD (35 in the intervention group, 35 in the control group).
- **Intervention Group:** Received eight 21-minute HRM sessions over four weeks (two sessions per week) during routine hemodialysis, in addition to usual care.
- **Control Group:** Received usual care only (routine dialysis nursing care) without HRM.
- **Data Collection Time Points:**
  - T0: Baseline (before the first session).
  - T1: Mid-intervention (after the 4th session).
  - T2: Post-intervention (after the 8th session).

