## 8. ETHICAL CONSIDERATIONS

- Ethical approval was obtained from the relevant institutional review board.
- Written informed consent was obtained from all participants prior to enrollment.

- Participation was voluntary, with the right to withdraw at any time without affecting their medical care.
- Confidentiality of participant data was strictly maintained (no names or identifiers are recorded in data collection tools).

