## **9. STATISTICAL ANALYSIS PLAN**

- Normality Testing: Shapiro-Wilk test will be used to assess the normal distribution of continuous variables.
- Within-Group Comparisons: Parametric tests (e.g., Repeated Measures ANOVA) for normally distributed data, and non-parametric tests (e.g., Friedman test) for non-normal data across the three time points (T0, T1, T2).
- Between-Group Comparisons: Independent t-test or Mann-Whitney U test to compare post-intervention scores between the intervention and control groups.
- Multiple Comparisons: Bonferroni correction will be applied for post-hoc pairwise comparisons to control Type I error.
- Associations: Chi-square or Fisher's exact tests will be used to examine relationships between demographic/clinical characteristics and HRM effectiveness.
- Clinical Significance: Minimal Clinically Important Difference (MCID) will be calculated to determine the practical relevance of fatigue and anxiety score improvements. Analysis will be performed using SPSS.

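### If any T2 score is missing, the only between-arm test drops that patient, and the plan names no analysis set or missing-data method that would prevent it

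*Combined protocol and SAP*

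**What the plan says.** Section 6 (Methodology) describes a "Randomized Controlled Trial (RCT) with a 1:1 allocation ratio" and gives the sample as "70 adult patients receiving MHD (35 in the intervention group, 35 in the control group"). It does not say whether the 70 are patients enrolled, randomised or analysed. Scores are taken at baseline (T0), at T1, "Mid-intervention (after the 4th session"), and at T2, "Post-intervention (after the 8th session").

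Section 9 (Statistical Analysis Plan) names two families of test, to be run in SPSS:

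- Within group, if normality fails: "non-parametric tests (e.g., Friedman test) for non-normal data across the three time points (T0, T1, T2"). Where normality is accepted, the plan turns instead to "Parametric tests (e.g., Repeated Measures ANOVA) for normally distributed data".
- Between groups: "Independent t-test or Mann-Whitney U test to compare post-intervention scores between the intervention and control groups".

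Section 8 (Ethical Considerations) states: "Participation was voluntary, with the right to withdraw at any time without affecting their medical care".

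No section defines an analysis population, an imputation or modelling approach to missing scores, a rule for incomplete questionnaires, follow-up after withdrawal, or a dropout allowance.

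**The concern.** The research question is a comparison of massage plus usual care with usual care alone after eight sessions. The only test in the plan that makes this comparison uses T2 scores alone. A patient who contributes T0 and T1 but not T2 is left out of it, and nothing in the plan brings that patient back in.

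This matters because the control arm receives usual care without massage, so patients know their allocation, and both outcomes are self-reported scales. Whether a patient stays to T2 may then depend on how that patient is doing. If that dependence differs between arms, the patients compared at T2 are no longer the groups formed by randomisation. The T1 score, which may help to predict who leaves, is available but unused.

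The within-group tests have a separate weakness: classical repeated measures ANOVA and the Friedman test need all three scores. That costs data in a small trial, but it does not affect the randomised comparison, because those tests do not compare the arms.

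**Working it through.** **The plan's own figure.** 35 + 35 = 70 is consistent. It cannot be re-derived, because no significance level, power, effect size, SD or dropout rate is stated. Every missingness rate and correlation below is an assumption.

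**Who is lost from which test.** Suppose that, of 70 patients, one misses T1 only, one misses T2 only and one misses both.

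- Between-arm T2 test: 70 − 2 = 68 analysed.
- Within-group tests: 70 − 3 = 67 analysed in total.

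A gap at T1 alone leaves the patient in the between-arm test. Fatigue and anxiety are separate scales, so a gap on one does not remove the patient from the other.

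**Two patterns of loss.**

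- *Withdrawal with no later scores.* If 10% (20%) leave before T1, every test uses 70 × 0.90 = 63 (70 × 0.80 = 56) patients, and the same ones.
- *Independent intermittent gaps.* With 10% missing at each of T1 and T2, 0.90² = 0.81, or about 28 of 35 per arm, remain in the within-group tests. With 15%, 0.85² = 0.7225, or about 25 of 35. The T2 test would keep 0.90 × 35 = 31.5 or 0.85 × 35 = 29.75 per arm on average.

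**Bias in the T2 comparison under one-sided selective loss.** Assume no true effect, scores standardised so that higher is better, a T1–T2 correlation of 0.6, and no loss in the control arm. In the massage arm, half of the patients in the worst 20% (40%) of T1 scores leave before T2, a loss of 10% (20%).

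| Step | 10% loss | 20% loss |
|---|---|---|
| Mean T1 of those who leave | −1.40 | −0.966 |
| Mean T1 of those who stay | 0.10 × 1.40 / 0.90 = 0.156 | 0.20 × 0.966 / 0.80 = 0.24 |
| Shift at T2 (× 0.6) | 0.093 SD | 0.145 SD |
| Standard error of the T2 difference | √(1/31.5 + 1/35) = 0.246 | √(1/28 + 1/35) = 0.254 |
| Shift in standard errors | 0.38 | 0.57 |

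At an assumed two-sided 5% level, and ignoring the small change in variance, the false-positive rate is the sum of two normal tails:

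- 10% loss: beyond 1.96 − 0.38 = 1.58 (5.7%) and below −2.34 (1.0%), in total 6.7%.
- 20% loss: beyond 1.96 − 0.57 = 1.39 (8.2%) and below −2.53 (0.6%), in total 8.8%.

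**Does the alternative remove it?** In 20,000 simulated trials of 35 per arm under these assumptions, the completers comparison was shifted by 0.095 and 0.143 SD. A likelihood estimate that conditions on T1 was shifted by 0.002 and −0.001 SD. This is as expected, because in this scenario loss depends only on an observed score.

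**The case against.** The strongest reply is that nothing in the documents shows that data will be missing. Follow-up lasts four weeks, sessions take place during routine dialysis, and the withdrawal right is a standard consent provision. With complete data all 70 patients are analysed and the issue disappears. This stands, and the point is conditional for that reason.

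A reader might go further in four ways that the documents do not support:

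- *That the plan has chosen a completers analysis.* It has not. The within-group tests are given as examples, and the plan is silent on imputation rather than excluding it. The defect is an unspecified approach whose default is complete cases.
- *That losses from the ANOVA or Friedman test damage the randomised comparison.* These are within-group tests. Only a missing T2 score reaches the between-arm comparison.
- *That each test will use a different set of patients.* This follows from intermittent gaps. If withdrawn patients simply give no further scores and leave before T1, all tests use the same patients.
- *That the result will be biased towards massage.* The illustration puts selective loss in one arm and among poor responders only. Similar selection in both arms would largely cancel, and loss of poor scorers from the control arm would bias against massage.

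There are also fair objections to a mixed model. It brings a normality assumption to scales bounded at 0–52 and 0–63, where the plan had kept rank tests in reserve. Sections 6 and 8 are written partly in the past tense, so it may be too late to change data collection. Section 9 is mostly in the future tense, so on its wording the analysis can still be changed.

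**Conclusion.** The concern holds in conditional form. Once any T2 score is missing, the plan's only between-arm test excludes that patient and ignores the T0 and T1 scores, and no stated rule prevents this. The loss from the within-group tests is a separate and lesser matter; the 28 (25) of 35 per arm applies only to those tests and only under independent gaps of 10% (15%).

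Under the one-sided scenario the shift is about 0.09 to 0.14 SD, and the false-positive rate rises from 5% to roughly 7–9%. That is modest, and it rests on assumed attrition, an assumed correlation and loss confined to one arm. The change is still worth making: it is cheap, it uses data already planned, and a missing-data method chosen after the results are seen would carry little weight.

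**What to change.** Amend Section 9 as follows.

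1. Define the analysis set as all randomised patients in their allocated arm.
2. For each outcome (FACIT-Fatigue and Ar-BAI), fit one likelihood-based mixed model in SPSS MIXED to every available T0, T1 and T2 score, with arm-by-time terms. Take the T2 arm contrast as the between-group result.
3. Report the T2 t-test or Mann-Whitney test on completers as supportive.
4. Add a multiple-imputation sensitivity analysis in which imputed T2 scores in the massage arm are made worse over a range fixed in advance. The direction of worsening differs by scale: lower on FACIT-Fatigue, higher on Ar-BAI.
5. If data collection is still open, keep collecting T1 and T2 questionnaires from patients who stop the massage sessions, where consent allows.

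**Cost.** Items 1 to 4 need SAP wording and analysis time in software the plan already names, with no extra visits. There are two models rather than one, and the sensitivity analysis needs its own imputation step, because the mixed model does not produce imputed values. The model assumes that scores are missing at random, which item 4 probes, and that residuals are approximately normal on bounded scales. Residuals should be checked, and the supportive Mann-Whitney test gives a partial cross-check on normality.

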## **3. HYPOTHESES**

There is a statistically significant difference in fatigue and anxiety levels between hemodialysis patients receiving HRM plus usual care and those receiving usual care alone.

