## **4. OBJECTIVES**

- Assess baseline fatigue and anxiety levels prior to HRM.
- Evaluate the effect of the HRM program on fatigue and anxiety post-intervention.
- Compare post-intervention changes between the intervention and control groups.
- Examine associations between socio-demographic/clinical characteristics and HRM effectiveness.

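### The sole between-arm test uses unadjusted post-intervention scores; adjusting for the T0 score already scheduled would add precision at almost no cost

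*Combined protocol and SAP*

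**What the plan says.** Section 6 describes a "Two-group parallel Randomized Controlled Trial (RCT) with a 1:1 allocation ratio", with "70 adult patients receiving MHD (35 in the intervention group, 35 in the control group") and assessments at T0, T1 and T2. T2, after the eighth session, is the time point labelled post-intervention. Section 4 lists baseline assessment of both outcomes ("Assess baseline fatigue and anxiety levels prior to HRM") and, as the third objective, "Compare post-intervention changes between the intervention and control groups".

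Section 9 has one line on comparing the arms: "Independent t-test or Mann-Whitney U test to compare post-intervention scores between the intervention and control groups". It names no baseline covariate, change score or group-by-time term. T0 is used under the heading for within-group comparisons, through repeated measures ANOVA or "non-parametric tests (e.g., Friedman test) for non-normal data across the three time points (T0, T1, T2"). The remaining lines cover normality testing, Bonferroni-corrected post-hoc pairs, associations with patient characteristics, and the MCID. None of them specifies a baseline-adjusted comparison of the arms.

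**The concern.** The third objective speaks of changes between arms, whereas the test that would address it uses T2 scores alone. Change over time is examined only inside each arm, and placing one arm's within-group p-value beside the other's is not a randomised comparison. The randomised evidence therefore rests on the single unadjusted test.

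With 35 per arm, two things follow. Variation in T2 that the patient's own T0 score could explain stays in the error term, so the confidence interval is wider than the scheduled data allow. And if the arms happen to differ at T0, part of that difference carries into the T2 comparison with nothing in the analysis to remove it. At stake is how precisely the trial can estimate the massage effect on fatigue and anxiety.

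**Working it through.** **The plan's own figure.** The total of 70 cannot be reproduced, because the documents give no alpha, power, effect size, SD or dropout rate behind it.

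**Inputs from the documents.** 35 per arm, 1:1 randomisation, both scales measured at T0 and T2 (Sections 5 to 7).

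**Assumed inputs, not in the documents.** Two-sided alpha 0.05 (the hypothesis in Section 3 is non-directional), a true effect of 0.5 SD, equal SDs, complete data, and a T0–T2 correlation ρ of 0.3, 0.5 or 0.7.

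**Step 1, standard error.** In SD units, the unadjusted T2 difference has SE = √(2/35) = 0.239. With T0 as covariate, SE = √(2/35) × √(1 − ρ²).

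**Step 2, power and detectable effect.** These come from the noncentral t distribution with noncentrality 0.5/SE, on 68 degrees of freedom (t-test) or 67 (ANCOVA).

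**Step 3, equivalent size.** The unadjusted test would need 35/(1 − ρ²) patients per arm for the same precision: 35/0.91 = 38.5, 35/0.75 = 46.7, 35/0.51 = 68.6.

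| Analysis | SE (SD) | Power at 0.5 SD | Detectable at 80% power (SD) | Equivalent n per arm |
|---|---|---|---|---|
| Unadjusted | 0.239 | 54% | 0.68 | 35 |
| ANCOVA, ρ = 0.3 | 0.228 | 58% | 0.65 | 38.5 |
| ANCOVA, ρ = 0.5 | 0.207 | 66% | 0.59 | 46.7 |
| ANCOVA, ρ = 0.7 | 0.171 | 82% | 0.49 | 68.6 |

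**Step 4, simulation check.** In 20,000 simulated trials per setting (normal data, 35 per arm), power was 54% for the unadjusted t-test and 57%, 65% and 82% for ANCOVA at the three correlations. A t-test on change scores reached 42%, 54% and 76%. All three estimators averaged about 0.50 SD when the true effect was 0.5 SD, and each rejected in about 5% of trials when there was no effect.

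**Step 5, chance imbalance.** The T0 difference between arms also has SE 0.239 SD. The chance that it exceeds 0.3 SD in either direction is 2 × [1 − Φ(0.3/0.239)] = 0.21. Given an imbalance of exactly 0.3 SD, the expected shift in the unadjusted T2 difference is ρ × 0.3 = 0.09, 0.15 or 0.21 SD at ρ = 0.3, 0.5 or 0.7.

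**The case against.** The strongest reply is that the planned test is sound. Randomisation makes the expected T0 difference zero, so the expected difference in T2 scores equals the expected difference in change. The simulation bears this out, and it shows type I error is held. The hypothesis is also worded in terms of levels: "There is a statistically significant difference in fatigue and anxiety levels between hemodialysis patients receiving HRM plus usual care and those receiving usual care alone". A T2 comparison tests exactly that. This stands.

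A reader might infer that the plan fails to answer the third objective, or that its estimate is biased. The documents support neither. The mismatch between changes in Section 4 and scores in Section 9 is one of wording; both target the same expected effect. The shift in step 5 is conditional on one realised allocation, is equally likely in either direction and averages to zero. The unadjusted standard error already reflects it.

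It is also fair to object that the gain depends on a correlation the documents do not give. At ρ = 0.3 it is modest: 4 percentage points of power and an SE about 5% smaller. The same scale in the same patients four weeks apart makes a clearly positive correlation plausible, but the larger gains cannot be presented as established.

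Finally, ANCOVA needs a provision for non-normal data, which Section 9 plans for and which matters for a bounded score such as Ar-BAI (0–63). This is a condition on the remedy and does not argue against adjustment.

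**Conclusion.** The point holds as a matter of efficiency and of aligning the analysis with the objective. The between-arm analysis leaves out a baseline score that the trial schedules for both outcomes. Under the assumptions listed, it forgoes a share of information of about ρ²: 9%, 25% or 49% at correlations of 0.3, 0.5 and 0.7. It also leaves any chance baseline imbalance uncorrected. The direction is secure for any correlation of practical size; the amount is not, because alpha, effect size and correlation are all assumed. That every patient will have a T0 score is likewise the plan, as completeness is not reported.

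The planned test remains valid, so this is a strong recommendation for a nearly free improvement. It falls short of a flaw that would invalidate the trial's conclusion.

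**What to change.** In Section 9, replace the between-group line as follows.

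- **Main analysis:** for FACIT-Fatigue and for Ar-BAI separately, ANCOVA of the T2 score on arm and the T0 score of the same scale, reporting the adjusted mean difference with its 95% confidence interval. With T0 in the model, the arm effect is the same whether the outcome is expressed as score or change, so this also serves the third objective. A bare change-score t-test would match that objective's wording but is less precise than ANCOVA, and less precise than the planned test when ρ is below 0.5.
- **Non-normal data:** judge normality on the model residuals. If they are clearly non-normal, use rank-based ANCOVA, or bootstrap or robust confidence intervals, with the choice stated in advance.
- **Sensitivity analysis:** keep the unadjusted t-test or Mann-Whitney U test.
- **Timing:** record the change in a dated SAP amendment made before the arms are compared. Section 9 is largely in the future tense, but Sections 6 and 8 describe treatment and consent in the past tense. If outcomes have already been seen, disclose that.

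The cost is one error degree of freedom (68 to 67) and the amendment. No new data are needed, and the basic ANCOVA runs in SPSS, the package already named. Adjusting for dialysis unit, if more than one enrols, is a separate option that uses further degrees of freedom and is not needed to resolve this point.

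### Holm's step-down correction would give the T0, T1 and T2 pairwise comparisons the same Type I error control as the planned Bonferroni and would never reject less; the gain is confined to secondary within-group contrasts

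*Combined protocol and SAP*

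**What the plan says.** Section 9 plans a within-group analysis of each outcome "across the three time points (T0, T1, T2"), by repeated-measures ANOVA if the data look normal and by Friedman's test if not. For the follow-up it says: "Bonferroni correction will be applied for post-hoc pairwise comparisons to control Type I error". No step-down variant is mentioned, so ordinary Bonferroni is the natural reading. The section does not state alpha, the number of comparisons, or the family that the correction covers. The within-group analyses are the natural source of pairwise comparisons.

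The middle assessment is defined in Section 6 as "T1: Mid-intervention (after the 4th session"). The trial's hypothesis (Section 3) is a difference between arms. Section 9 tests it separately, by "Independent t-test or Mann-Whitney U test to compare post-intervention scores between the intervention and control groups".

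**The concern.** Plain Bonferroni holds every contrast to alpha/3 whatever the other contrasts show. Holm relaxes the threshold for the remaining contrasts once the smallest p-value has passed, and keeps the same guarantee. The plan's stated purpose, control of Type I error, is therefore met equally well by a method that never finds less.

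The contrasts that can gain most are T0-T1 and T1-T2. They show whether change has appeared by the fourth session and whether it continues to the eighth. If change is gradual, each of these steps is smaller than the overall T0-T2 change, and the fixed threshold costs them most.

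**Working it through.** **Inputs from the documents.** Three time points (Sections 6 and 9), so 3 × 2 / 2 = 3 pairwise contrasts per scale and arm. Sample size: "70 adult patients receiving MHD (35 in the intervention group, 35 in the control group"), so n = 35 for a within-arm contrast. No alpha, power, effect size, SD or correlation is stated, so there is no planned power figure to reproduce for these comparisons.

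**Assumptions.** Two-sided family-wise alpha of 0.05; paired t-tests on complete data; changes in units of a common SD. Correlations are either 0.7 for adjacent visits and 0.49 for T0-T2 (set A) or 0.6 for every pair (set B).

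**Step 1: thresholds.**
- Bonferroni: all three p-values against 0.05/3 = 0.0167.
- Holm: ordered p-values against 0.05/3 = 0.0167, 0.05/2 = 0.025 and 0.05/1 = 0.05, stopping at the first failure.

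**Step 2: Holm never rejects less.** Any p-value that passes 0.0167 also passes whichever Holm threshold it meets, and so do all smaller p-values. Both methods test the smallest p-value at 0.0167, so the chance of at least one rejection is identical.

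**Step 3: error control is the same.** If m of the nulls are true, the first true null that Holm tests meets a threshold no larger than 0.05/m. By the Bonferroni inequality the family-wise error is then at most 0.05. No extra assumption is needed.

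**Step 4: simulated power, n = 35** (20,000 to 40,000 runs per scenario).

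| Means at T0/T1/T2 (SD) | Correlations | Contrast | Bonferroni | Holm |
|---|---|---|---|---|
| 0/0.30/0.60 | A | each adjacent | 42% | 54% |
| 0/0.30/0.60 | A | T0-T2 | 83% | 84% |
| 0/0.35/0.70 | A | each adjacent | 57% | 70% |
| 0/0.30/0.60 | B | each adjacent | 31% | 40-41% |
| 0/0.30/0.30 | A | T0-T1 | 42% | 44% |
| 0/0.40/0.40 | A | T0-T1 | 70% | 72% |
| 0/0.40/0.40 | B | T0-T1 | 55-56% | 59% |
| 0/0.10/0.20 | A | each adjacent | 5% | 6% |

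The gain is largest when both steps are real and of moderate size. It shrinks when the change is complete by T1 or when the steps are very small.

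The chance that all three contrasts are significant, which is the pattern of change by session 4 and further change by session 8, goes from about 16% to 33% in the first scenario.

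**Step 5: false rejections.** With no change at all, the chance of any rejection was the same for both methods, about 4.2 to 4.6% across runs. No Bonferroni rejection was lost by Holm in any scenario. If T0-T1 is truly null and T2 is shifted by 0.8 SD, T0-T1 is falsely rejected in about 1.5 to 1.7% of runs under Bonferroni and 4.7 to 5.0% under Holm. Holm uses the 5% allowance that Bonferroni leaves idle, and does not exceed it.

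**Step 6: omnibus gate.** If the pairwise tests are run only after a significant repeated-measures ANOVA, the comparison hardly moves. With equal correlations of 0.7 and steps of 0.30 SD, adjacent power is still about 42% against 54%.

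**The case against.** **This is not an error, and no trial conclusion depends on it.** That stands. A reader might infer that the choice weakens the test of hand reflexology itself. It does not: Section 3 states a between-arm hypothesis, and Section 9 tests it with a two-sample comparison that this correction does not enter. Contrasts within one arm cannot separate a massage effect from change over time. The objective "Evaluate the effect of the HRM program on fatigue and anxiety post-intervention" concerns T2, and T0-T2 gains only about 1 point with equal steps.

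**The loss is not certain.** This stands too. A reader might infer that real changes will be missed, but the documents give no effect size, SD or correlation. They support only a possibility whose size depends on assumptions, and equal steps are among the patterns that favour Holm. It would also be too strong to say that the adjacent contrasts are the only use of T1, since T1 enters the ANOVA or Friedman test as well.

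**Holm can itself be beaten.** For three means, Shaffer's procedure (alpha/3, then alpha, alpha) keeps the same control and gives about 59% adjacent power in the first scenario, against 54% for Holm and 42% for Bonferroni. Where to stop between simplicity and power is a matter of judgement. This does not remove Holm's gain over the stated method.

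**Bonferroni gives simple simultaneous intervals.** This is a genuine advantage, and it matters because Section 9 intends to judge improvements against a minimal clinically important difference.

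**Conclusion.** The point holds as an optional gain in efficiency for secondary comparisons. Bonferroni is valid and does what the plan says it is for. Holm gives the same family-wise protection, never rejects less, and so can detect adjacent-visit changes that the stated method would miss.

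Under two-sided 0.05, n = 35 per arm and correlations of 0.6 to 0.7, all assumed except n, the size is:
- about 9 to 13 points of power per adjacent contrast with equal steps of 0.30 to 0.35 SD;
- about 1 to 4 points for T0-T1 if the whole change of 0.3 to 0.4 SD occurs by T1;
- about 1 point or less with steps of 0.1 SD;
- about 1 point for T0-T2 with equal steps;
- nothing for the chance of at least one significant pair, or for the between-group test.

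**What to change.** Replace the multiple-comparisons sentence in Section 9 with:

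*Post-hoc pairwise comparisons of T0, T1 and T2 will be adjusted by the Holm step-down procedure within each scale and arm (three comparisons; ordered p-values multiplied by 3, 2 and 1 and kept non-decreasing).*

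The family should be named as scale and arm. There are two arms, so a family defined by scale alone would contain 2 × 3 = 6 contrasts; the multipliers would then start at 6 and the gains above would not apply. The same rule serves the paired tests that follow either the ANOVA or the Friedman test.

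The cost is one sentence, fixed before results are seen, and a short calculation from the unadjusted p-values. No extra data are needed. The downside is that Holm has no simple matching simultaneous confidence intervals, so any intervals reported would stay unadjusted or Bonferroni-based, and the SAP should say which. The change does not deal with multiplicity across the two scales in the between-group tests, which is a separate matter.

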## **5. DEFINITION OF TERMS (Operational)**

- Hand Reflexology Massage (HRM): A 21-minute organized protocol applied by nurses to specific reflex zones on both hands (solar plexus, diaphragm, adrenal gland, kidney, pituitary gland, and heart) during dialysis sessions.
- Fatigue: Measured using the Arabic FACIT-Fatigue Scale (13 items, scored 0-52). Higher scores indicate lower fatigue levels and better quality of life.

- Anxiety: Measured using the Arabic Beck Anxiety Inventory (Ar-BAI) (21 items, scored 0-63). Scores are classified into minimal (0-7), mild (8-15), moderate (16-25), and severe (26-63) anxiety.

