## 7. STUDY INSTRUMENTS

1. Demographic and Clinical Characteristics Questionnaire (age, gender, education, income, duration of HD, etc.).
2. Arabic FACIT-Fatigue Scale (Version 4).
3. Arabic Beck Anxiety Inventory (Ar-BAI).

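### Objective 4 is tested only with chi-square or Fisher's exact tests, which forces two numeric scores into categories and can cost substantial power

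*Combined protocol and SAP*

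**What the plan says.** Section 4 (Objectives) lists as its fourth aim: "Examine associations between socio-demographic/clinical characteristics and HRM effectiveness". Section 9 (Statistical Analysis Plan) gives one line on method: "Chi-square or Fisher's exact tests will be used to examine relationships between demographic/clinical characteristics and HRM effectiveness". The within-group line in the same section offers its tests as examples. The associations line does not, and no correlation, regression or interaction model appears anywhere.

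Section 5 (Definition of Terms) defines both outcomes as numeric scores, FACIT-Fatigue from 0 to 52 and Ar-BAI from 0 to 63. For anxiety only, it adds bands: "Scores are classified into minimal (0-7), mild (8-15), moderate (16-25), and severe (26-63) anxiety". No bands are given for fatigue, for change in either score, for age or for duration of HD.

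Section 7 (Study Instruments) lists the characteristics: "Demographic and Clinical Characteristics Questionnaire (age, gender, education, income, duration of HD, etc". It does not say which are recorded as numbers and which in bands. Section 9 also states that "Minimal Clinically Important Difference (MCID) will be calculated to determine the practical relevance of fatigue and anxiety score improvements", without a value and without linking it to the association tests. Section 6 (Methodology) sets the size at "70 adult patients receiving MHD (35 in the intervention group, 35 in the control group".

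**The concern.** A contingency-table test uses only category membership. A patient whose FACIT-Fatigue score rises by 1 point and one whose score rises by 15 count the same if both fall on the same side of the cut. Ordered characteristics such as education are treated as unordered. Nothing in the plan requires this: the repeated-measures and between-group analyses in Section 9 use the same two scores whole, with rank tests as the fallback.

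Two things are at stake. First, this is the only analysis that answers Objective 4. With 35 or 70 patients, a table with no significant cell pattern could be reported as no relationship when the test had little chance of finding a moderate one. Second, HRM effectiveness is not defined as a category, and apart from the four anxiety bands no cut-points are fixed. The result for fatigue, and for any characteristic recorded as a number, would then depend on cuts that could be chosen after the data are seen.

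**Working it through.** **Inputs from the documents.** 70 patients, 35 per arm (Section 6); scores 0-52 and 0-63 (Section 5); chi-square or Fisher's exact tests only (Section 9). The documents give no alpha, power, SD, effect size or association strength, so the figure of 70 cannot be reproduced. For orientation, 35 per arm gives 80% power at an assumed d of 0.67, two-sided 5%.

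**Assumptions.** Two-sided 5%; normal variables; no dropout; numeric characteristic split at its median; outcome cut at a fixed threshold giving 50% responders; uncorrected chi-square. n=35 stands for the HRM arm alone and n=70 for all patients.

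**Large-sample efficiency.** A median split of one normal variable keeps 2/π = 0.64 of the information. Splitting both keeps (2/π)² = 0.41.

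**Numeric characteristic, both variables cut.**
- Full scale, Fisher z approximation: power ≈ Φ(atanh(ρ)·√(n−3) − 1.96).
  - n=35, ρ=0.4: 0.4236 × √32 = 2.40, giving Φ(0.44) ≈ 67%.
  - n=70, ρ=0.3: 0.3095 × √67 = 2.53, giving Φ(0.57) ≈ 72%.
- Cut: the responder proportion above or below the median is 0.5 ± arcsin(ρ)/π. Power ≈ Φ((Δ − 1.96·SE₀)/SE₁).
  - n=35 (17 vs 18), ρ=0.4: 0.631 vs 0.369, Δ=0.262, SE₀=0.169, SE₁=0.163, giving Φ(−0.43) ≈ 34%.
  - n=70 (35 vs 35), ρ=0.3: 0.597 vs 0.403, Δ=0.194, SE₀=0.1195, SE₁=0.117, giving Φ(−0.34) ≈ 37%.

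**Binary characteristic, only the outcome cut, d=0.8.**
- Full scale: t-test with noncentrality d·√(n₁n₂/n).
  - n=35: 0.8 × √(17×18/35) = 2.37 on 33 df, power 63%.
  - n=70: 0.8 × √17.5 = 3.35 on 68 df, power 91%.
- Cut: Φ(±0.4) = 0.655 vs 0.345, Δ=0.311.
  - n=35: (0.311 − 1.96×0.169)/0.161 = −0.13, about 45%.
  - n=70: (0.311 − 1.96×0.1195)/0.114 = 0.67, about 75%.

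**Arm-by-characteristic interaction, 70 patients.** With residual SD 1 and characteristic SD 1, the SE of the slope difference is about √(2/32) = 0.25. A slope difference of 0.6 gives 0.6/0.25 − 2.00 = 0.40, so power is about 66%. A difference of 0.4 gives −0.40, about 34% (36% by simulation).

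**Simulated power.** Repeat runs agree within about two points. The small-sample chi-square comes out slightly below the hand approximations.

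| Setting (assumed) | Full scale | Cut |
|---|---|---|
| Numeric, n=35, ρ=0.4 | 69% | 31% |
| Numeric, n=70, ρ=0.3 | 73% | 34% |
| Binary, n=35, d=0.8 | 63% | 44% |
| Binary, n=70, d=0.8 | 91% | 73% |
| Interaction, n=70, slope difference 0.6 | 66% | 30% |

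**Outside the moderate range (simulated).** At ρ=0.1, power is 8% vs 6% (n=35) and 12% vs 7% (n=70). At n=70 it is 100% vs 99% for ρ=0.7, and 99.9% vs 97.4% for a binary characteristic with d=1.2.

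**Sensitivity to the cut (simulated).** Cutting the outcome at the sample median instead of a fixed threshold changes the chi-square power at ρ=0.3 from about 18% to 13% (n=35) and from 34% to 39% (n=70). Fisher's exact test on the latter table has 22%.

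**The case against.** The best counter-argument has four parts.

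- **Recording of the characteristics.** The questionnaire may record age, income or HD duration in bands. If so, the test discards nothing on that side. Gender needs no cut in any case. This stands: the double-cut figures apply only to characteristics held as numbers. The outcome is cut regardless.
- **Ready-made categories.** The anxiety bands are fixed in advance, and an MCID is planned. Either could define a meaningful response. This stands in part: a late choice of cut is not shown for anxiety bands, but neither device is tied to the association tests, and fatigue has no bands.
- **What Objective 4 needs.** A regression of T2 on T0 and characteristics finds predictors of outcome, not of benefit from HRM. This stands, so the interaction with arm has to be the main term. Even on the full scale its power is only about 36% at a slope difference of 0.4, so a null result would stay uninformative.
- **Importance.** The objective is absent from the research question and hypothesis, and the main comparisons use full scores. This also stands and limits the weight of the point.

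A reader might infer that the plan loses about half its power across the board. The documents do not support that. They give no association strength, and the relative loss runs from about 55% (69% to 31%) to about 20% (91% to 73%) in the table, and is smaller still for strong associations at n=70.

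**Conclusion.** The point holds, with a conditional size. As written, the associations line makes it necessary to categorise both numeric outcomes, and any characteristic recorded as a number, although the same plan keeps the scores whole elsewhere. Under moderate assumed associations the cost is about 36 to 39 percentage points of power when both variables are cut, including the interaction case, and about 18 to 19 points when only the outcome is cut. These figures assume normal data, a two-sided 5% level and 50% responders. They shrink towards nothing for very weak associations and, in 70 patients, for very strong ones.

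Two further inferences would go too far. The efficacy conclusion is not put at risk, because the between-arm tests use the full scores. Nor would a full-scale analysis make Objective 4 well powered, because modest interactions would still usually be missed. This is an inexpensive improvement to a secondary objective.

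**What to change.** Replace the associations line in Section 9 with:

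> For each characteristic in turn, the T2 FACIT-Fatigue and Ar-BAI scores will be analysed on their full scale in all 70 patients by linear regression on T0 score, arm, the characteristic and the arm-by-characteristic term. The interaction estimate with its 95% CI is the measure of association with HRM effectiveness. Characteristics recorded as numbers will be entered as continuous, and those recorded in categories as factors. If residuals are clearly non-normal, robust or bootstrap intervals will be used. Chi-square and Fisher's exact tests will be used only to describe categorical variables. The analysis is exploratory, and a null result will not be read as no relationship.

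Section 7 should also state how age, income and duration of HD are recorded.

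The cost is a few sentences and a model that SPSS already fits, with no extra patients or data. The drawbacks are that the model assumes approximate linearity for numeric characteristics and is less simple to present than a cross-table. Descriptive tables by category can stay.
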